3.3.2 Total Number of Study Sites/Total Number of Subjects Projected

Surveys will be administered at the following fifteen US investigative sites: Children's Hospital of Philadelphia (*Philadelphia, PA*), Children's Healthcare of Atlanta (*Atlanta, GA*), C.S. Mott Children's Hospital (*Ann Arbor, MI*), Ann & Robert H Lurie Children's Hospital of Chicago (*Chicago, IL*), Arkansas Children's Hospital (*Little Rock, AR*), Children's Medical Center of Dallas (*Dallas, TX*), Texas Children's Hospital (*Houston, TX*), Primary Children's Medical Center (*Salt Lake City, UT*), Children's Hospital of Michigan (*Detroit, MI*), Lucile Packard Children's Hospital Stanford (*Palo Alto, CA*), St. Jude Children's Research Hospital (*Memphis, TN*), Seattle Children's Hospital (*Seattle, WA*), Children's Hospital Colorado (*Denver*), Nemours/A.I. duPont Hospital for Children, and DFCI/Boston Children's Hospital (*Boston, MA*). These sites were chosen based on geographic location, their substantial AML/MDS patient volume, and the variation in primary strategy of neutropenia management.

We expect approximately 278 subjects across all sites to be enrolled and approximately 236 subjects to be evaluable (118 patients and 118 caregivers).

3.4 Study Population

The study population will include all AML and MDS patients who are receiving a planned frontline chemotherapy course at any of the fifteen pediatric institutions across the US starting June 1, 2016. Patients discharged within 3 days after chemotherapy completion will be categorized as 'early discharge' to outpatient management during neutropenia. Patients remaining in the hospital more than 3 days after chemotherapy completion will be categorized as inpatient management.

Caregivers of these patients will also be included.

3.4.1 Enrollment Criteria

3.4.1.1 Inclusion Criteria

- 1) Participants will be enrolled as patient-caregiver dyads. The patient must be:
 - Less than 19 years of age at initial AML/MDS diagnosis.
 - Receiving standard intensive AML frontline chemotherapy starting June 1, 2016 or after.
 - Able to read English or Spanish, if 8 years of age or older
- 2) Participants will be enrolled as patient-caregiver dyads. The caregiver must be:
 - Able to read English or Spanish.
 - The legal guardian of a patient receiving standard intensive AML frontline chemotherapy starting June 1, 2016 or after .
- 3) Parental/caregiver informed consent and, if appropriate, child assent.

3.4.1.2 Exclusion Criteria

- Patients being treated for relapsed AML
- Patients with Acute Promyelocytic Leukemia (APML)
- Patients undergoing stem cell transplant (SCT)
- Patients receiving reduced intensity frontline chemotherapy

Any violations of these criteria will be reported in accordance with IRB Policies and Procedures.

4 STUDY PROCEDURES

4.1 Participant Identification

Local study investigators (pediatric oncologists and study coordinators) at each of the fifteen participating pediatric institutions will communicate on a weekly basis with their inpatient leukemia service to identify AML or MDS patients potentially eligible for study enrollment. Once identified, study personnel will review each patient for study eligibility criteria.

4.2 Screening Visit

The eligibility criteria for participation will be confirmed prior to approaching for consent. Eligible patients interested in the study will be approached for consent at any time from AML/MDS diagnosis through last day of chemotherapy in the treatment course under study. In some cases, the patient's caregivers may not be present in the hospital to provide consent. In these cases, study personnel will obtain verbal consent from the caregivers and child assent (if appropriate).

4.3 Visit 1

Visit 1 will occur prior to the last day of chemotherapy administration in the course. This visit will include:

- 3 baseline health-related quality of life (HRQOL) PedsQL™ survey modules (core, cancer, and fatigue)
- 2 Brief demographic surveys to capture covariates unavailable in the medical record
- 1 Financial toxicity survey

Surveys will be administered via paper or a smart device and will last a total of 15-30 minutes per respondent. In the case that the child is 5 years of age or older, the child self-report and parent proxy-report scales will be separately administered to the child and caregiver, respectively. If the child is between 5 and 8 years of age, Study Personnel will read the survey questions to the patient. There is an illustrated response aid for these young patients. These age-specific PedsQL instruments have been previously validated. The child will indicate their answer as 'Not at all', 'Sometimes', or 'A lot' by pointing to a smiling, middle, or frowning face, respectively. If the child is under 5 years of age, only the parent-proxy version will be administered. Caregivers will also be asked to complete the demographic covariate surveys and the financial toxicity survey during Visit 1. The brief demographic surveys capture covariates unavailable in the medical record, such 'patient race/ethnicity', 'patient/parent education level', and 'parent marital status'. The financial toxicity survey assesses the financial situation of the caregiver/family.

4.4 Visit 2

Visit 2 will occur within the period after absolute neutrophil count recovery and ideally prior to the start of the subsequent course of chemotherapy, but no later than the last day of chemotherapy in that next treatment course. For the small number of patients who will begin the next course of chemotherapy before count recovery, Visit 2 will occur within the period from one day prior to the start of chemotherapy in that next treatment course and no later than the last day of chemotherapy in that course. This visit will include:

- 3 follow-up health-related quality of life (HRQOL) PedsQL™ surveys (core, cancer, and fatigue)
- 1 PCO survey
- 1 Financial toxicity survey

All surveys will be administered via paper or a smart device and will last a total of 15-30 minutes per respondent. In the case that the child is 5 years of age or older, the PedsQL child self-report and parent proxy-report scales will be administered to the child and caregiver, respectively. If the child is between 5 and 8 years of age, Study Personnel will read the survey questions to the patient. There is an illustrated response aid for these young patients. These age-specific PedsQL instruments have been previously validated. The child will indicate their answer as 'Not at all', 'Sometimes', or 'A lot' by pointing to a smiling, middle, or frowning face, respectively. If the child is under 5 years of age, only the parent-proxy version will be administered. Caregivers will also be asked to complete the PCO

survey at follow-up. The PCO survey assesses dimensions such as parental stress and anxiety, patient's sleep behaviors, impact on siblings, and hospital discharge teaching practices. In addition, caregivers will be asked to complete the financial toxicity survey again at follow-up. The caregiver completing the follow-up assessments must be the same caregiver who completed the baseline assessments. We will provide a \$50 gift card to each child-parent dyad upon completion of the PCO survey, financial toxicity survey, and follow-up quality of life surveys. If the child and caregiver do not complete both visits, they will only be compensated a portion of the \$50 for the visits they do complete.

4.5 Subject Completion/Withdrawal

Subjects may withdraw from the study at any time without prejudice to their care. They may also be discontinued from the study at the discretion of the Investigator for lack of adherence to the study plan.

4.5.1 Early Termination Study Visit

Child-caregiver dyads who withdraw from the study during or prior to completion of the follow-up surveys will only be compensated a portion of the \$50 for the visits they do complete.

5 STUDY EVALUATIONS AND MEASUREMENTS

5.1 Screening and Monitoring Evaluations and Measurements

5.1.1 Screening

The following information will be utilized by local study investigators prior to participant approach:

- Date of birth
- Specific leukemia diagnosis and date
- Planned treatment regimens
- Ability to read English or Spanish for all caregivers and for patients 8 years of age or older

Some information will be retained for screened patients who do not enroll to document the reasons for exclusion. Specifically, we will be retaining age, leukemia diagnosis and date, treatment course, and whether the patient received reduced intensity chemotherapy.

5.1.2 Medical Record Abstraction

Medical record abstraction will be performed as per the related Protocol 15-012074 Aim 1: Managing neutropenia in pediatric AML protocol. The table below includes a complete list of the data elements to be abstracted. St. Jude Children's Research Hospital is not participating in Aim 1 and therefore will follow the abstraction process outlined in the Aim 3 Protocol Addendum. The abstracted data elements will be linked to the quality of life and PCO data described in the current protocol.

Variable

Date of birth
Sex
Patient race/ethnicity
Date of AML (or MDS) diagnosis
Age at AML (or MDS) diagnosis
Vital status
Date of death or date of last known follow-up
Location of death (in hospital or at home)
AML subtype
AML risk classification and cytogenetics
Hospital admission start/stop dates
Chemotherapy course number
Chemotherapy regimen and start/stop dates
Course start/stop dates
On COG protocol or similar clinical trial?
Documentation of deviation from planned chemotherapy course
Presence/type of central line
MRD post courses and dates of MRD obtained
Post course remission status
Daily max. fever; how was temperature taken
Infections during chemotherapy courses
ICU care during chemotherapy courses
ANC measurements post chemotherapy
Dates of ANC measurements
Dates and results of microbiological cultures/PCRs onset during post chemotherapy course follow-up
Mucositis severity by course
Systemic antimicrobial prophylaxis at each course
Height, weight, and body surface area at end of chemotherapy course
Nutritional status/supplemental support requirements on day of chemotherapy completion
Ability to practice oral hygiene
Insurance status at course start (private, self-pay, public, other)
English spoken?
Home address
Availability of working telephone
Automobile/taxi voucher requirements
Caregiver's relation to patient
Caregiver's marital status
If caregiver is married, relation between caregiver's spouse and patient
Date of relapse
Site of relapse
Date of transplant
Type of transplant

5.1.3 Evaluations and Measures

Three evaluation tools will be utilized over the two study visits: 2 demographic covariate surveys, PedsQL™ scales, and a PCO Survey.

- **Demographic covariate survey**

The following patient-level information will be obtained via survey to capture covariates unavailable or less readily available in the medical record:

- Patient race/ethnicity
- Parental employment status
- Household income
- Parental and patient education level
- Number of adults living in the primary residence
- Number of other children living in the primary residence

- Demographic covariate survey II

The following patient-level information will be obtained via survey to capture covariates unavailable or less readily available in the medical record:

- Parent/legal guardian who signed informed consent
- Relation to patient (i.e. mother, father, other)
- Parent/legal guardian marital status

- **PedsQL™**

HRQOL will be assessed using the following validated PedsQL™ scales:

- The 23-item multidimensional 4.0 Generic Core Scales:
 - Physical functioning (8 items)
 - Emotional functioning (5 items)
 - Social functioning (5 items)
 - School functioning (5 items)
- The 18-item multidimensional Fatigue Scale:
 - General fatigue (6 items)
 - Sleep/rest fatigue (6 items)
 - Cognitive fatigue (6 items)
- The 27-item multidimensional 3.0 Cancer Module:
 - Pain/hurt (2 items)
 - Nausea (5 items)
 - Procedural anxiety (3 items)
 - Treatment anxiety (3 items)
 - Worry (3 items)
 - Cognitive problems (5 items)
 - Perceived physical appearance (3 items)
 - Communication (3 items)

- **Financial toxicity survey**

- 11-item survey that assesses the financial situation of the caregiver/family.

Items inquire about:

- Having enough money to cover cost of child's treatment

- Out-of-pocket expenses exceeding their expectations
- Worrying about future financial problems
- Feeling like have no choice about amount spent on care
- Feeling frustrated that cannot work or contribute as much as usual
- Satisfaction with current financial situation
- Ability to meet monthly expenses
- Feeling financially stressed
- Concern about keeping job and income
- Overall control of financial situation

The format, instructions, response scale and scoring methods for the three PedsQL scales are identical. Each is available in parallel child self-report and parent proxy-report formats. Child self-report versions include ages 5-7 years, 8-12 years and 13-18 years. Parent proxy report versions include ages 1-2 years, 2-4 years, 5-7 years, 8-12 years and 13-18 years. In this study we will administer the Child Self-Report versions of the scales for children 5 years of age and older in addition to the Parent Proxy-Report versions.

A 5-point Likert response scale is used across child self-report for ages 8-18 and parent proxy-report (anchored by 0 = never a problem to 4 = almost always a problem). Responses to each question are used to assemble a score.

Each of these scales demonstrates internal reliability acceptable for group comparisons (PedsQL™ Generic Core Total Scale Score [Cronbach's α = 0.88 child, 0.93 parent report]; Multidimensional Fatigue Total Scale Score [α = 0.89 child, 0.92 parent report]; most Cancer Module Scales [average α = 0.72 child, 0.87 parent report]) (29). These scales have also been shown to be sensitive to change over time in children with cancer (30).

- **PCO Survey**
 - Pediatric Inventory for Parents-Difficulty scales (PIP-D)-(42 items)
 - Parental stress and anxiety (9 items)
 - Sleep Disturbance Scale for Children (SDSC): Disorders of Initiating and Maintaining Sleep domain (DIMS) (7 items)
 - Impact on Siblings (7 items)
 - Hospital Discharge Teaching Practices (4 items)

The PCO survey will be completed by the parent during study Visit 2. The PCO includes established measures of parental stress (PIP-D) and sleep disturbance in children (SDSC DIMS) as well as survey questions designed to measure the incidence and sources of parental financial stress; sources of parenting, emotional, domestic and financial support; the incidence and nature of sibling behavioral change, and the receipt of training prior to discharge from the hospital.

The PIP-D assesses stress-related difficulty with events faced by parents of children with serious illness across four domains: communication (e.g., with child, partner, or health care team), emotional functioning (e.g., impact of illness on sleeping and mood), child's medical care (e.g., carrying out medical regimen), and role functioning (e.g., impact of illness on

parent's ability to work and care for other children). All items are rated on a five-point Likert scale from 1 (not at all difficult) to 5 (extremely difficult) (31).

The SDSC DIMS assesses sleep indices such as latency and duration, night awakenings, and reluctance to go to bed. All items are measured on a five-point Likert scale, in which 1=never, 2=occasionally, 3=sometimes, 4=often, and 5=always. The SDSC is reported to have high internal consistency among both healthy ($\alpha=0.79$) and sleep disordered participants ($\alpha=0.71$), as well as high test-retest reliability ($r=0.71$) (32).

- **Financial toxicity survey**

The financial toxicity survey will be completed by the parent at both baseline and follow-up (Visit 1 and Visit 2). The survey includes 11 statements about the financial situation of the caregiver/family in relation to the child's treatment adapted from existing literature (37). A 5-point Likert response scale is used for the parent to indicate the degree to which they agree with each statement (0 = Not at all; 1 = A little bit; 2 = Somewhat; 3 = Quite a bit; 4 = Very much).

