6.3 Statistical Methods

6.3.1 Analysis of Primary Outcomes of Interest

Propensity score analyses will be used to adjust for potential confounding by baseline covariates. First, bivariate analyses will be performed to evaluate relationships between each baseline covariate and neutropenia management strategy as well as each outcome of interest. Next, propensity scores will be derived from the predicted probabilities estimated from logistic regression models of the use of outpatient versus inpatient management during neutropenia conditional on all baseline factors determined to be true confounders (i.e., those associated with both exposure and outcome) and those determined to be potential confounders (i.e., those associated only with the outcome interests). Patients will then be stratified into five groups using quintiles of the estimated propensity score. The distributions of exposure within the quintiles will be examined for sufficient sample sizes and balance. Within each stratum, the patients managed as outpatient and those managed as inpatient will ideally have similar values of the propensity score and likewise the distribution of measured baseline covariates will be comparable between them.

PedsQL™ items will be reverse scored and linearly transformed to a scale of 0 to 100 such that higher scores will be reflective of better HRQOL. The PedsQL™ total score will be calculated as the sum of the item-specific scores divided by the number of answered items (33, 34).

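### Sources of family support are asked only at Visit 2, too late for the baseline propensity score, so part of any confounding by support may remain, chiefly in outcomes measured only at Visit 2

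*Combined protocol and SAP*

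**What the plan says.** **Where support is asked.** Section 5.1.3 describes the PCO survey as including questions on "sources of parenting, emotional, domestic and financial support". On timing it says: "The PCO survey will be completed by the parent during study Visit 2". Table 1 and section 4.4 agree.

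**When exposure is set.** Section 3.4: "Patients discharged within 3 days after chemotherapy completion will be categorized as 'early discharge' to outpatient management during neutropenia". Everyone else counts as inpatient. Section 4.3: "Visit 1 will occur prior to the last day of chemotherapy administration in the course". Section 4.4: "Visit 2 will occur within the period after absolute neutrophil count recovery and ideally prior to the start of the subsequent course of chemotherapy". The few patients who start the next course before count recovery have Visit 2 around that course. So Visit 1 precedes the classification and Visit 2 follows it.

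**How confounding is handled.** Section 6.3.1: "Propensity score analyses will be used to adjust for potential confounding by baseline covariates". The score is estimated "conditional on all baseline factors determined to be true confounders", together with factors linked to outcome alone, and is used in quintiles. Section 6.3.2 adjusts the PCO models by those quintiles.

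**What is known about the home at baseline.** The Visit 1 demographic surveys record items such as "Number of adults living in the primary residence", other children in the home, marital status, employment, income and education. The abstraction list in section 5.1.2 adds insurance, telephone and transport. The financial toxicity survey is given at both visits. None of these asks directly who helps the family.

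**The concern.** The study is not randomised, so its protection against bias depends on measuring, before discharge, what separates families who go home early from those who stay. Whether a caregiver has help is a plausible candidate. It may affect whether a neutropenic child can be managed at home. It may also affect parental stress, the child's sleep, siblings and proxy-rated quality of life.

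An answer given at Visit 2 cannot do this job. Home management may itself bring in relatives or friends, so Visit 2 support may be partly a consequence of the strategy. Adjusting for it could remove part of the effect under study or introduce a new bias. Leaving it out leaves whatever confounding the proxies miss. If better-supported families are over-represented among early discharges, outpatient management could look somewhat better for reasons unrelated to setting.

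The outcomes differ in exposure to this. PIP-D, SDSC DIMS and sibling change are measured once, at Visit 2, so no baseline value absorbs pre-existing differences. PedsQL is measured at both visits and tested through the group-by-time interaction.

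**Working it through.** **1. The plan's own figure (section 6.4).** Inputs: 47 outpatients, 71 inpatients, SD 20, significance level 0.05 (taken as two-sided). SD of change = 20 × √(2(1 − ρ)); standard error = SD of change × √(1/71 + 1/47) = SD of change × 0.188.

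- ρ = 0: SD of change 28.28. Power for 15.0 points is 80.5% (normal) or 79.9% (t).
- ρ = 0.8: SD of change 12.65. Power for 6.8 points is 81.6% (normal) or 80.9% (t).

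Both agree with the stated 80%. Each benchmark goes with its own SD of change.

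**2. Assumed inputs.** The documents give no strength for either link. Assume half of families have strong support, 40% go home early (the 40% is the plan's), an odds ratio of 1.5 to 3 between support and early discharge, and an effect of support on the outcome of 0.3 to 0.8 SD.

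**3. Imbalance in support.** Let p and q be the early-discharge probabilities with and without strong support. Then (p + q)/2 = 0.40 and the odds ratio fixes p. Prevalence of support is 0.5p/0.4 among outpatients and 0.5(1 − p)/0.6 among inpatients. Bias in SD units = gap × effect.

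| Odds ratio | p | Outpatient | Inpatient | Gap (unrounded inputs) | Bias at 0.3 SD | Bias at 0.8 SD |
|---|---|---|---|---|---|---|
| 1.5 | 0.449 | 0.561 | 0.460 | 0.101 | 0.030 SD | 0.081 SD |
| 2 | 0.482 | 0.603 | 0.431 | 0.171 | 0.051 SD | 0.137 SD |
| 3 | 0.528 | 0.660 | 0.393 | 0.267 | 0.080 SD | 0.214 SD |

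**4. Outcomes measured only at Visit 2.** The standard error of a group difference is 0.188 SD. A bias of 0.030 SD shifts the test statistic by 0.16; 0.214 SD shifts it by 1.14. With no true effect of setting, the two-sided false-positive rate for one continuous outcome rises from 5% to between 5.3% and 20.6%, before any adjustment.

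**5. PedsQL.** If support shifts the score equally at both visits, the shift cancels in the group-by-time term and the bias is 0. Only an effect on change counts. Reading 0.3 to 0.8 SD as SDs of change:

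- ρ = 0.8: 0.030 × 12.65 = 0.4 points to 0.214 × 12.65 = 2.7 points, against 6.8.
- ρ = 0: 0.030 × 28.28 = 0.9 points to 0.214 × 28.28 = 6.0 points, against 15.0.

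The upper end is demanding: at ρ = 0.8 it needs support alone to move change by 0.8 × 12.65 = 10.1 points.

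**6. Allowing for the proxies.** If baseline proxies removed 25% to 50% (again assumed), the PedsQL range at ρ = 0.8 would be 0.2 points (half of 0.38) to 2.0 points (three quarters of 2.70). For a Visit 2-only outcome it would be 0.015 to 0.160 SD.

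**The case against.** **Support may be meant as an outcome.** The plan puts these questions in its patient-centered outcomes survey and labels other surveys as covariate surveys. A reader might infer that a covariate was put at the wrong visit, or that the items have no analytic use. The documents support neither reading. Support is absent from the list in section 6.1, but section 6.3.2 says generally that PCO will be related to management strategy, and Visit 2 is the right time for an outcome. This stands. It argues for keeping the Visit 2 questions, not against a baseline measure.

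**Proxies exist.** A reader might infer that all confounding by support is left in the comparison. That goes too far. Household composition, marital status, income, transport and the whole financial toxicity survey are available at baseline, and the primary model also adjusts for measured confounders still unbalanced. This stands in part: section 6.3.1 does not list the candidate covariates, so use of the proxies is possible but not assured.

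**Hospital policy drives discharge.** Section 1.1 reports that about 60% of COG institutions always keep patients in hospital, and section 3.3.2 says sites were chosen partly for variation in strategy. Where policy is fixed, family support cannot affect discharge. This stands and may push the pooled odds ratio towards 1.

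**The size could be overstated.** A reader might multiply 0.214 SD by 20 and set 4.3 points against 6.8. That mixes scales: 6.8 holds only at correlation 0.8, where the SD of change is 12.65. The consistent figure is 2.7.

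**Conclusion.** The concern holds in a limited form. Direct information on family support arrives only after exposure, cannot validly enter the baseline propensity score, and has no direct counterpart at Visit 1. Part of any confounding by support may therefore remain after the proxies are used. The one sensitivity analysis against bias named in section 6.2 varies the discharge-day threshold, which addresses misclassification and not an unmeasured confounder.

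The weight falls on PIP-D, SDSC DIMS and sibling change. For the continuous scores, the illustrative bias before adjustment is 0.03 to 0.21 SD. For PedsQL the concern is narrower: zero if support has a stable effect on level, and 0.4 to 2.7 points at correlation 0.8 if it affects change.

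All these sizes rest on assumed prevalence, odds ratio and effect. That support drives early discharge is plausible but is not stated in the documents. Confidence in the magnitude is low. The case for acting rests on how little a baseline measure costs in a study that depends on covariate adjustment.

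**What to change.** Add the support-source questions to the Visit 1 caregiver survey, worded for the period before discharge, and keep them at Visit 2 as a PCO. Name the Visit 1 answers, alongside the household and financial proxies, as candidate covariates for the propensity model. State that Visit 2 support answers will not be used for adjustment.

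Adding is better than moving. Moving would delete a follow-up measure, and because the documents do not say which block holds the support questions, it could disturb the financial-stress questions behind a listed secondary outcome.

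**Cost.** A survey-form amendment and a few more caregiver questions at the lighter visit. By the listed counts the caregiver answers about 68 PedsQL + 9 demographic + 11 financial = 88 items at Visit 1 (counting each demographic topic as one item), against 68 + 69 PCO + 11 = 148 at Visit 2. Dyads already enrolled will lack baseline support, and the plan must say how that is handled, for example by a missing category.

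If enrolment is too far advanced, the sponsor can still name the household covariates, rule out Visit 2 support as a covariate, and add a sensitivity analysis for unmeasured confounding, such as an E-value.
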